Study Title:
**Social Ecological Based Smoking Cessation Intervention in Public Housing
Neighborhoods**

R01HL090951

Date: 8/09/2018

Statistical Analyses.

Preliminary Analysis. Univariate descriptive statistics and frequency distributions will be calculated as appropriate for all variables. These analyses will identify departures from distributional assumptions for proposed procedures. If departures are identified, appropriate transformations of data will be applied, or alternative analysis procedures (e.g., semi-parametric or nonparametric) will be employed. Baseline values for demographic and other putative prognostic variables will be compared for imbalance across the two treatment conditions (TX, C). These analyses will identify potential confounding variables to be used as covariates in subsequent analyses. Putative prognostic variables that will be investigated through these descriptive analyses include age, income, education, nicotine dependence score, and depression score. *To investigate potential limits on generalizability, we will compare demographic and other baseline characteristics of the dropouts with those who were completers.*

Premature exits (drop-outs) and missing data. *In order to minimize potential bias due to missing observations, we will carefully document why data are missing, which will involve contacting via telephone, if necessary, those who do not return for follow-up assessments to attempt to ascertain smoking status, and reason(s) for dropout. We will adopt several approaches to dealing with missing data for the ITT analysis set. For the primary dichotomous cessation outcomes, we will impute outcome status in two ways: (1) by considering dropouts as smokers, and (2) using a stochastic regression imputation developed by Hedeker [143] taking different source of variation into account. For analyses of continuous variables using a single outcome (e.g., change from baseline in nicotine dependence score), we will use the multiple imputation methods of Little [144] and Rubin [145]. For longitudinal data, where appropriate, we will employ longitudinal data methods (e.g., mixed models, random regression, or hierarchical linear models) which allow for missing data [143,146]. We will carry out sensitivity analyses by comparing the results of analyses using different methods of imputation to evaluate the role of missing data in the study's conclusions. The implications of the sensitivity analyses will be discussed in presentations of study findings. In addition, we will model the dichotomous outcome, missing/not missing end-of-study score, using logistic regression to determine if "missingness" is related to treatment group and/or initial level of the given outcome variable (baseline score). We will also use information on drop-outs as one of the outcome measures of effectiveness of the interventions being compared. We will make every attempt to keep subjects in the study and to obtain required measurements.*

Analyses for Primary Aim.

Aim #1. To test the effectiveness of a multi-level intervention (*Sister to Sister*) on smoking cessation outcomes in female smokers residing in public housing neighborhoods.

Hypothesis 1.1: As compared to the control group, women receiving the *Sister to Sister Intervention* will have higher 7-day point prevalence quit rates at 6-and 12-months.

Hypothesis 1.2: As compared to the control group, women receiving the *Sister to Sister Intervention* will have higher 6- and 12-month prolonged abstinence.

To evaluate the relationships between intervention outcomes and intervention status (TX or C), we will use a generalized linear mixed models (GLMM) approach (*or equivalently hierarchical linear models [HLM], random regression models [RRM], or mixed effects models [MEM]*) with treatment assignment as the primary independent variable and measures of

effectiveness as the dependent variable [146]. This approach accommodates a wide range of distributional assumptions for continuous and categorical outcome variables, including binary (e.g., smoking cessation/no cessation - the primary outcome), count, and ordinal measures, as well as multilevel data such as longitudinal measurements on subjects and a possible cluster effect within neighborhoods [143,146]. These analyses allow for measurement of subjects at different time points, missing data, and time varying or invariant covariates.

In the GLMM analyses, treatment (TX vs C) and measurement time (6 months and 12 months) will be included as a fixed effect, a term representing neighborhood (the cluster effect) will be included in the model as a random effect in order to account for correlation among women within the same neighborhood, *with a pair-specific fixed intercept parameter to represent each neighborhood pair* [148]. The statistical test of primary interest will be the F-test for the treatment x time interaction, which will reflect a difference in change between the intervention and control groups over the course of the study.

In further analyses, putative covariates will be added to the model to examine whether the intervention remained statistically and clinically associated with cessation after controlling for the potential covariates. Each covariate considered for inclusion will be examined individually for a relationship with cessation outcomes. In the second step, those variables with a p value < .25 will be included in an initial model. Next, the potential confounder variable in the initial model with highest p value will be removed and the model will be run again. If the removal of the potential confounder variable does not result in a significant reduction in model fit (as indicated by a change in the model -2 log likelihood), then the variable is removed from further steps. The removal and subsequent testing of change in model fit will be repeated until all non-significant potential confounders are tested. Potential covariates include demographic variables (i.e., age, income, education), nicotine dependence score, depression score, body mass index, perceived stress, social smoking influences, *social ties, neighborhood cohesion, neighborhood smoking prevalence, neighborhood stress*, and time dependent covariates of self efficacy, spiritual well-being, social support, and *cessation resources*.

The magnitude of intervention effect sizes (e.g., differences in 7-day point prevalence proportions between TX and C groups, and odds ratios for cessation) will be estimated using 95% confidence intervals (95%CI). Effect size estimates allow evaluation of the "clinical" or practical significance/relevance of the study findings.

Analyses for Secondary Aims.

Aim #2. To evaluate the effect of the *Sister-to-Sister* intervention on individual (self-efficacy, spiritual well-being), interpersonal (social support), and neighborhood (cessation resources) factors and to determine if these factors mediate the effect of treatment on smoking cessation outcomes.

Hypothesis 2.1: As compared to the control group, women receiving the *Sister to Sister* intervention will have greater improvement in individual factors (self-efficacy, spiritual well-being), interpersonal factors (social support), and neighborhood factors (*cessation resources*) at 6-and 12 months.

Hypothesis 2.2: Positive changes in individual factors (self-efficacy, spiritual well-being), interpersonal factors (social support, and neighborhood factor (*cessation resources*)) will mediate the effect of the 6- and 12-month cessation outcomes in women receiving the *Sister to Sister* intervention.

A generalized linear mixed models (GLMM) approach, as described for the Primary Aim, will be used for Aim 2. To examine the effect of treatment (TX vs C) on individual factors (self-efficacy, spiritual well-being), interpersonal factors (social support), *and neighborhood factors (cessation resources)* [Hypothesis 2.1], each of the individual variables within the factors will be used individually as the outcome (dependent) variables in the GLMM. As described above, treatment and measurement time will be considered fixed effects, and neighborhood will be

considered a random effect, with a *pair-specific fixed intercept parameter* to represent each neighborhood pair. Additional covariates, as described above, will be added to the model to determine the effect of treatment on these outcomes adjusted for the effect of the covariates.

The analyses for Hypothesis 2.2 address the question of whether the individual (self-efficacy, spiritual well-being), interpersonal (social support), and neighborhood factors (cessation resources) explain (mediate) the relationship between the outcome (6- and 12-month cessation) and the intervention (Sister-to-Sister). In mediator analyses, it is posited that variation in a given independent variable (intervention) accounts for variation in the mediators (self-efficacy, spiritual well-being, social support, cessation resources) and variations in mediators account for variations in outcome (6-and 12-month cessation). For these analyses, we will follow the methods of Baron and Kenney [149], Holmbeck [150], and Kraemer [151]. GLMM analyses as outlined above will evaluate the relationship between the outcome (6- and 12-month cessation) and the intervention (Aim 1). Next, the relationship between intervention and the putative mediator variables (self-efficacy, spiritual well-being, social support, cessation resources) will be evaluated as described for Hypothesis 2.1. Finally, the mediating effect of self-efficacy, spiritual well-being, social support, cessation resources on a significant treatment effect will be evaluated in a GLMM model that simultaneously regresses treatment (TX vs C) and the putative mediating variables on outcome (smoking cessation). A significant smoking cessation/treatment relationship that becomes nonsignificant following the addition of the putative mediator covariable suggests that the latter accounts for (mediates) the former observed relationship. For example, we conclude that the relationship between treatment and smoking cessation is mediated by self efficacy if the variable representing self efficacy is significant and a previously significant treatment effect becomes nonsignificant in the multivariable model containing both.

102,10:1513-1684.

144. Little RJA, Rubin DB (1987) *Statistical Analysis with Missing Data*. 1987. J. Wiley & Sons, New York.

145. Little RJA, Rubin DB (1987) *Statistical Analysis with Missing Data*. 1987. J. Wiley & Sons, New York.

146. Gibbons R. *Longitudinal Data Analysis*. 2006. John Wiley and Sons, Inc. New York.

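### Aim 1's primary test is not tied to one cessation endpoint or one missing-data rule, so it exists in four unranked versions with no success rule

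*SAP*

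**What the plan says.** Three parts of the SAP bear on this.

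- **Hypotheses under the Primary Aim.** Hypothesis 1.1 is that women receiving the intervention "will have higher 7-day point prevalence quit rates at 6-and 12-months". Hypothesis 1.2 is that they "will have higher 6- and 12-month prolonged abstinence". The two stand side by side and neither is placed first.
- **Premature exits (drop-outs) and missing data.** "For the primary dichotomous cessation outcomes, we will impute outcome status in two ways": first "by considering dropouts as smokers", and second "using a stochastic regression imputation developed by Hedeker [143] taking different source of variation into account". The section numbers these but does not rank them. It then adds: "We will carry out sensitivity analyses by comparing the results of analyses using different methods of imputation". It also promises that the implications will be discussed when findings are presented.
- **Analyses for Primary Aim.** The model description refers to "smoking cessation/no cessation - the primary outcome", giving neither a definition of cessation nor a time. The model holds the 6- and 12-month measurements together. The F-test for the treatment-by-time interaction is named as the test of primary interest, with no endpoint or missing-data rule attached.

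The SAP contains no hierarchy, alpha split, multiplicity adjustment or statement of what counts as success for Aim 1. It states no significance level. The only error-rate figure is the 95% confidence level used for effect sizes.

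**The concern.** A primary test gives one answer only if its outcome and its handling of missing data are fixed in advance. Here the test is named and both of these are left open.

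The versions need not agree. The plan itself treats point prevalence and prolonged abstinence as separate hypotheses. The SAP does not define prolonged abstinence. If it requires a sustained period without smoking, a woman who quits shortly before the 12-month visit succeeds on one endpoint and fails on the other. The two scorings can also diverge. One sets every dropout to smoker, the other lets some dropouts be imputed as abstinent, and the gap grows if dropout differs between arms.

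At stake is whether a positive result on one version, with nothing on the others, could be reported as meeting the primary aim. The plan as written neither permits nor forbids this, and the false-positive rate for the aim as a whole is not held at the level of a single test.

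**Working it through.** The SAP gives no sample size, power, alpha or family-wise error figure, so there is no stated number to reproduce.

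**Inputs from the SAP**

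- Endpoints under the primary aim: 2 (Hypotheses 1.1 and 1.2).
- Missing-data rules for those endpoints: 2.
- Named primary test: one treatment-by-time F-test per fitted model, covering both times.

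**Assumptions (not in the SAP)**

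- Two-sided 5% per test.
- Correlation between the test statistics of the two endpoints: 0.5 to 0.8.
- Correlation between the two scorings of one endpoint: 0.8 to 0.95.
- Statistics that differ in both respects correlate at the product of the two values, for example 0.5 × 0.8 = 0.40.
- Normal test statistics. With two arms and two times the interaction has one numerator degree of freedom, so its F is the square of a single statistic. Small-sample degrees of freedom from the number of neighborhoods are ignored.

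**Step 1: count.** 2 endpoints × 2 scorings = 4 versions of the named test.

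**Step 2: ceiling under independence**, 1 − 0.95^k.

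- k = 2 (two endpoints, one scoring): 1 − 0.95² = 0.0975.
- k = 4 (two endpoints, two scorings): 1 − 0.95⁴ = 0.1855.

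**Step 3: correlated tests.** From 400,000 simulated draws per setting, the chance that at least one |z| exceeds 1.96 with no true effect:

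| Endpoint correlation | Scoring correlation | Two endpoints, one scoring | Two endpoints, two scorings |
|---|---|---|---|
| 0.5 | 0.8 | 0.091 | 0.140 |
| 0.7 | 0.9 | 0.084 | 0.117 |
| 0.8 | 0.95 | 0.078 | 0.100 |

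So the range is about 8–9% for the endpoints alone and 10–14% once the second scoring is added. Looser correlations of 0.3 and 0.7 gave 0.095 and 0.157.

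**Step 4: if time-specific contrasts were also used to claim success.** The count would be 2 × 2 × 2 = 8. The independence ceiling is 1 − 0.95⁸ = 0.337. With correlations between times of 0.5, 0.6 and 0.8 added to the three rows above, the simulated values were 0.241, 0.195 and 0.151. The SAP does not specify these contrasts as tests, so this is a conditional figure and not the plan's own error rate.

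**Step 5: after the fix.** One endpoint, one scoring and one contrast give one test at 5%. If the other endpoint is tested only after the first succeeds, the chance of any false claim across the two stays at or below 5%. If the sponsor prefers two co-primary endpoints under one scoring, Bonferroni gives 0.05 / 2 = 0.025 each.

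**The case against.** The best case for the plan has four parts.

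1. **There is one named test.** The treatment-by-time F-test comes from a model holding both times, so 6 and 12 months are not separate primary tests. This stands. A reader might infer that any of eight results could carry the aim, but that count sets aside the test the SAP names. It does not bring the count below four, because the test is not tied to an endpoint or a scoring.
2. **No 6-month-only success is provided for.** A reader might infer that a 6-month point-prevalence result alone would meet Aim 1. The SAP specifies no such test, and the wording of both hypotheses can be read as requiring both times, which would lower the false-positive risk. That reading is not stated either, and it would still leave open whether both hypotheses must succeed.
3. **The imputation methods are to be compared and the implications discussed.** This is a real commitment and limits selective reporting. It does not say which scoring is the base case if they disagree.
4. **The singular and plural wording can be reconciled.** The phrase "binary (e.g., smoking cessation/no cessation - the primary outcome" sits in a list of variable types that the model can handle and may simply name the construct, with the plural naming its measures. That is fair. Taken alone, the wording is not a firm contradiction, and the point does not rest on it.

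A protocol that is not shown may name one primary endpoint. The choice of main missing-data rule, however, is a matter this SAP takes up and leaves unsettled.

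**Conclusion.** The concern holds in this form: Aim 1 has two unranked endpoints, each scored by two unranked missing-data rules, and the single named test is not attached to any of the four combinations. Under the assumed 5% level and correlations, the chance of at least one false significant result is about 10–14%, of which the two endpoints alone account for about 8–9%. These figures depend on assumed inputs. The count of four and the absence of a success rule do not.

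Higher figures apply only if time-specific contrasts are also used to claim success, which the SAP neither specifies nor excludes. That opening exists because an interaction over 6 and 12 months tests a difference in change, while the hypotheses claim higher quit rates at those times. The plan should be changed, but it does not commit the trial to selective reporting.

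**What to change.** In the missing-data section and the Analyses for Primary Aim section:

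- Name one primary endpoint and one primary missing-data rule, for example 7-day point prevalence with missing counted as smoking.
- Make the other imputation a named sensitivity analysis that cannot replace the primary result.
- Test the other endpoint next, in fixed order, at the same alpha, and state that alpha.
- In the same edit, state which treatment contrast and which time carry the primary test, so that the F-test and the hypotheses of higher quit rates agree. Without this, naming an endpoint and time would leave the SAP with two competing primary tests.

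Nothing in the SAP favors one endpoint or order over another, so that choice is the sponsor's.

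The cost is SAP wording only. Given the contrast chosen, the first test loses no power. The downside is that a result below a failed step becomes supportive only.

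### The missingness model names no neighborhood or pair term and has no usable baseline predictor for cessation; separately, dropout as an effectiveness measure overlaps with counting dropouts as smokers (minor)

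*SAP*

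**What the plan says.** In the SAP section *Premature exits (drop-outs) and missing data*, the missingness check models "missing/not missing end-of-study score, using logistic regression to determine if" being missing depends on either of two predictors. One is the treatment group; the other is the "initial level of the given outcome variable (baseline score"). No neighborhood or pair term is named. The next sentence is a separate commitment: "We will also use information on drop-outs as one of the outcome measures of effectiveness of the interventions being compared". It gives no definition, model or rank for that measure.

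The same section sets two imputations for the cessation outcomes. The first counts dropouts as smokers; the second is a stochastic regression imputation. It also plans telephone contact to learn the smoking status of women who do not return.

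Under *Analyses for Primary Aim*, the outcome GLMM is specified differently: "a term representing neighborhood (the cluster effect) will be included in the model as a random effect", because women in one neighborhood may be correlated, "with a pair-specific fixed intercept parameter to represent each neighborhood pair". *Analyses for Secondary Aims* restates both terms for Aim 2. Aim 1 concerns "smoking cessation outcomes in female smokers residing in public housing neighborhoods".

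The SAP gives no cluster size, number of neighborhoods, intraclass correlation (ICC), retention rate or quit rate.

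**The concern.** The missingness model compares the two arms, and the arms appear to have been formed by neighborhood. The SAP does not say so in words; the neighborhood pairs and the cited reference on community intervention trials imply it. Women in one neighborhood may share reasons for being lost, such as moves, local staff or local events. A logistic model without a cluster term would then understate the standard error of the treatment coefficient, which is the reason the SAP itself gives for the random effect in its outcome models.

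The model's only other predictor is the baseline value of the outcome being analyzed. For cessation that value does not vary, so for the primary outcomes the model cannot say which women are lost.

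The third issue is independent of the model. If dropout is scored as effectiveness and is also counted as smoking, one retention difference appears as two results.

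**Working it through.** **Inputs.** From the SAP: the missingness model and its predictors, the neighborhood and pair terms of the GLMM, a population of smokers, and the imputation that counts dropouts as smokers. Assumed, because the SAP gives no figures: m = 20–30 women per neighborhood, ICC of missingness 0–0.05, and the quit and retention rates in step 3. There is no figure in the plan to reproduce.

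**1. Clustering.** Design effect DE = 1 + (m − 1) × ICC. Actual rejection rate of a nominal two-sided 5% test that ignores clustering = 2 × [1 − Φ(1.96/√DE)].

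Example: m = 20, ICC = 0.05 gives DE = 1 + 19 × 0.05 = 1.95, then 1.96/√1.95 = 1.40, and a rejection rate of 16.0%.

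The formula was checked by simulating beta-binomial missingness (20% missing in both arms, 20,000 runs per setting) and applying the pooled logistic Wald test.

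| m | ICC | DE | Formula | Simulated, 7 neighborhoods per arm | Simulated, 10 per arm |
|---|---|---|---|---|---|
| 20 | 0 | 1.00 | 5.0% | 4.9% | 4.9% |
| 20 | 0.01 | 1.19 | 7.2% | 7.2% | 7.2% |
| 20 | 0.02 | 1.38 | 9.5% | 9.3% | 9.0% |
| 20 | 0.05 | 1.95 | 16.0% | 15.8% | 15.9% |
| 30 | 0 | 1.00 | 5.0% | 4.9% | 4.8% |
| 30 | 0.01 | 1.29 | 8.4% | 8.3% | 8.4% |
| 30 | 0.02 | 1.58 | 11.9% | 12.2% | 11.6% |
| 30 | 0.05 | 2.45 | 21.1% | 20.8% | 21.2% |

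Neither calculation credits any gain from pairing. If paired neighborhoods resemble each other in missingness, the inflation is smaller.

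**2. Baseline term.** The design matrix has columns for intercept, treatment and baseline cessation status. The last is constant, so the matrix has rank 2 of 3 and the baseline coefficient cannot be estimated. What remains is logit P(missing) = α + β × treatment. The treatment coefficient is unaffected. For a continuous outcome such as the nicotine dependence score, the baseline varies and the term is valid.

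**3. Overlap with missing = smoker.** If a share q of women quit in each arm and a share d have unknown status, the counted quit rate is q × (1 − d).

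- q = 15% in both arms, retention 90% v 75%: 0.15 × 0.90 = 13.5%, and 0.15 × 0.75 = 11.25%, or about 11.3%.
- q = 20% in both arms, d = 10% v 30%: 0.20 × 0.90 = 18% and 0.20 × 0.70 = 14%. The odds ratio is (0.18/0.82)/(0.14/0.86) = 1.35.
- Equal d in both arms: no difference.

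In the first two cases the difference comes from retention alone, and the dropout measure would report the same retention gap again. Under the stochastic imputation dropouts are not fixed as smokers, so this arithmetic does not apply.

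**The case against.** **The SAP is silent on clustering here; it does not exclude it.** A logistic model with a neighborhood random effect is still logistic regression. That stands: this is an omission. But the SAP restates the terms for Aim 2 and not here, so two analysts could both follow the text and report different p-values.

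**The model is only a diagnostic.** A reader might infer that it supplies the dropout measure of effectiveness, so that an unclustered test would support an efficacy claim. The SAP does not link the two sentences. *Analyses for Primary Aim* assigns the GLMM to measures of effectiveness, and that would naturally cover dropout. A reader might also infer that this model decides whether missing data threaten the primary result. The SAP gives that role to comparing results across imputation methods; the logistic model is additional. An over-liberal test also errs on the cautious side for a bias check, because it flags differential missingness too often.

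**The SAP is not uniformly clustered elsewhere.** It would be wrong to say that every other arm comparison carries a neighborhood term. The baseline comparison in *Preliminary Analysis* names no model.

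**Baseline predictors of dropout are examined elsewhere.** *Preliminary Analysis* compares dropouts with completers on baseline characteristics. This is a partial answer. That comparison is descriptive and aimed at generalizability, and it does not supply the missing predictors to the model.

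**The double count is conditional.** It needs the first imputation and women whose status stays unknown after telephone contact. The primary test is the treatment-by-time interaction, so a gap of 13.5% v 11.3% at both visits would produce no interaction. That stands. The overlap would still shift the reported effect sizes, and it would reach the interaction test if the retention gap changed between 6 and 12 months.

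**Conclusion.** The point holds in a limited form, as a minor one.

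- The missingness model omits the neighborhood and pair terms. Fitted as written, its treatment test is too liberal whenever missingness clusters. The 7–21% range is an illustration on assumed cluster sizes and ICCs, without credit for pairing; at ICC 0 there is no inflation.
- For cessation the baseline predictor is constant and cannot be estimated. This follows from the population alone and needs no assumed figure. It does not affect the continuous scores.
- Dropout as an effectiveness outcome is undefined, and it overlaps with the first imputation for women of unknown status. The size of the overlap depends on the assumed quit and retention rates.

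None of this invalidates the primary analysis.

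**What to change.** In *Premature exits (drop-outs) and missing data*:

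1. Fit missingness with the neighborhood random effect and pair-specific intercepts of the main GLMM. If neighborhoods are few, use a small-sample reference distribution.
2. For the cessation outcomes, replace the baseline score with baseline variables the SAP already lists: nicotine dependence, depression, age, income and education. For missingness at 12 months, add 6-month smoking status where it is known. Keep the baseline score for continuous outcomes.
3. Report dropout by arm as retention, not as evidence of effectiveness, and state its overlap with the imputation that counts dropouts as smokers.

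The cost is SAP wording: the baseline variables are already named in the SAP, and 6-month smoking status is part of the primary outcome. The downside is that the missingness test becomes less likely to reach significance, so a non-significant result should not be read as showing that retention was balanced.

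### The declared primary test, treatment by time over 6 and 12 months, tests whether the treatment effect changes between follow-ups, not whether abstinence is higher as Hypotheses 1.1 and 1.2 claim.

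*SAP*

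**What the plan says.** Under Analyses for Primary Aim, Hypothesis 1.1 states that women receiving the intervention "will have higher 7-day point prevalence quit rates at 6-and 12-months", and Hypothesis 1.2 that they "will have higher 6- and 12-month prolonged abstinence", each compared with control.

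The GLMM paragraph of the same section says that "treatment (TX vs C) and measurement time (6 months and 12 months) will be included as a fixed effect", with neighborhood as a random effect and a fixed intercept for each neighborhood pair. It continues: "The statistical test of primary interest will be the F-test for the treatment x time interaction". The SAP's reading of this term is that it captures how far the two arms differ in their change during the trial. No baseline level of time is listed.

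The effect-size paragraph plans 95% confidence intervals for "differences in 7-day point prevalence proportions between TX and C groups, and odds ratios for cessation". It names no time point and declares no test.

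Under Analyses for Secondary Aims, the text for Hypothesis 2.2 says that the mediating effect "on a significant treatment effect will be evaluated in a GLMM model".

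**The concern.** Both primary hypotheses are about level: more women abstinent in the intervention arm at each follow-up. The named primary test is about change in the treatment effect from one follow-up to the next. The two can disagree in both directions. A benefit present at 6 months and fully held at 12 months, the result the trial hopes for, gives a null primary test. A benefit lost by 12 months can give a significant one.

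The report could then carry a primary p-value and a set of effect estimates that answer different questions, and readers would take the p-value as the verdict on the intervention. The mediation analysis is also affected. It starts from a significant treatment effect and refers back to the primary-aim GLMM, where the only test named is the interaction.

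**Working it through.** **Figures in the plan.** The SAP states no alpha, sample size, abstinence rates, within-woman correlation or intraclass correlation, so there is no figure to reproduce. Step 1 is algebra and needs none of these. Steps 2 to 5 are illustrations on assumed inputs.

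**Step 1: what the interaction measures.** With a logit link (not named in the SAP, but it fits the binary outcome and the planned odds ratios) and two times, the interaction has one numerator degree of freedom:

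(logit pT12 − logit pC12) − (logit pT6 − logit pC6) = log OR12 − log OR6 = log(OR12/OR6).

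If OR12 = OR6 this is 0, whether both equal 1 or both equal 3. A correctly sized test then rejects at the alpha rate for any sample size.

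**Step 2: formulas and assumptions.** Assume n = 200 per arm, within-woman correlation ρ = 0.5, two-sided 0.05, no clustering. For each arm, the variance of a logit at one time is 1/(n·p·q), with q = 1 − p, and the covariance of the two logits is ρ/(n·√(p6·q6·p12·q12)). Arms add. Power is Φ(|z| − 1.96) + Φ(−|z| − 1.96).

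**Step 3: lasting benefit, 16% v 8% at both times (OR 2.19).**
- Log OR at each time: −1.658 − (−2.442) = 0.784.
- Variance at one time: (1/0.1344 + 1/0.0736)/200 = 21.03/200 = 0.1051, SE 0.324.
- 12-month contrast: z = 0.784/0.324 = 2.42, power 68%.
- Average of the two times: variance 0.1051 × (1 + 0.5)/2 = 0.0789, SE 0.281, z = 2.79, power 80%.
- Joint 2-df test: noncentrality 0.784²/0.0789 = 7.8, power 71%.
- Interaction: estimate 0, SE 0.324, rejection 5%.

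**Step 4: benefit gone by 12 months, 20% v 10% then 10% v 10%.**
- Interaction estimate: 0 − log 2.25 = −0.811.
- Variance, intervention: (6.25 + 11.11 − 2 × 4.17)/200 = 0.0451. Control: (11.11 + 11.11 − 2 × 5.56)/200 = 0.0556. Sum 0.1007, SE 0.317.
- z = −2.56, power 72%. For ρ from 0.3 to 0.6 it is 58% to 81%. Rates of 20% then 10% allow a correlation of at most √(0.1 × 0.8/(0.2 × 0.9)) = 0.67.

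**Step 5: other patterns and clustering.**

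| Assumed pattern | Interaction | 12-month contrast | Average |
|---|---|---|---|
| 16% v 8% at both | 5% | 68% | 80% |
| Same, design effect 1.5 | 5% | 51% | 63% |
| Same, 500 per arm, design effect 1.5 | 5% | 88% | 95% |
| 20% v 10%, then 10% v 10% | 72% | 5% | 32% |
| 12% v 8%, then 20% v 8% | 45% | 92% | 76% |
| 20% v 12%, then 16% v 8% | 9% | 68% | 76% |

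The interaction does gain power when the odds ratio moves, as in the last three rows. With early harm (OR 0.4 then 1.0, control 10%, ρ = 0.5) it rejects in 65%, with no benefit at either visit.

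A simulation of a paired cluster design (assumed 8 pairs, 25 women per neighborhood, intraclass correlation 0.02, paired t-test on neighborhood risk differences) gave about 5% for the interaction, 43% for the 12-month contrast and 49% for the average under the lasting benefit. Under the fading benefit the interaction rejected in about 72%. A neighborhood effect shared by both times cancels from the interaction, so clustering weakens the level tests and leaves the interaction almost unchanged.

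**The case against.** **Baseline may be intended.** The SAP's gloss speaks of change over the course of the study, and Hypothesis 2.1, analysed with the same model, is about improvement. Abstinence at entry is 0% in both arms, so on a risk-difference scale a difference in change from baseline would equal a difference in level. This explains how the sentence may have arisen. It does not rescue it: the listed times exclude baseline, the aim concerns effects "on smoking cessation outcomes in female smokers residing in public housing neighborhoods", and when no one is abstinent at entry a baseline level has no finite logit and gives no usable interaction on the odds-ratio scale.

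**The treatment effect is already estimated.** The SAP makes treatment the main independent variable and plans confidence intervals for the group comparison. This stands: a reader would see the effect. But neither passage withdraws the one test declared primary. The mediation wording most naturally means the treatment term, which itself shows that the SAP elsewhere assumes a different test.

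**The calculation assumes within-woman correlation is modelled.** The model sentence lists only a neighborhood random effect, although the general description of the GLMM covers repeated measurements on subjects. Fitted literally, with ρ = 0.5, the interaction under a lasting benefit would reject in about 0.6% rather than 5%, and the fading figure would fall from 72% to about 42%. That makes the planned test worse. It also bears on the fix, because the average effect would then have a type I error near 11%.

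**The fading case is weaker evidence.** The 6-month part of Hypothesis 1.1 is true there, and the joint 2-df test would reject in about 82%. Agreed. The decisive case is the constant odds ratio.

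**Conclusion.** The point holds and must be fixed. As written, the primary test is neither necessary nor sufficient for Hypothesis 1.1 or 1.2. Under a constant odds ratio it has no power beyond alpha at any sample size, and this follows from the two listed times and a logit link alone. On another link it would still test change in effect between visits. The power percentages depend on assumed rates, sample size, correlation and design effect. They show the scale of the mismatch and are not estimates for this trial. Under a constant odds ratio the level tests outperformed the interaction in every setting tried.

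**What to change.** Replace the sentence naming the interaction with one such as: *The primary test of Hypotheses 1.1 and 1.2 is the treatment effect (TX v C) from this GLMM.* Then fix one form in advance:

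- (a) separate contrasts at 6 and 12 months with a stated multiplicity rule, for example 12 months first and then 6 months in fixed sequence, or both required at 0.05. This is closest to the wording of the hypotheses;
- (b) the average effect over the two times; or
- (c) the joint 2-df test, noting that it can reject on a 6-month effect alone.

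Keep the treatment by time interaction as a secondary test of whether the effect persists. State explicitly that the model accounts for correlation between a woman's two measurements; this is essential for (b). In the text for Hypothesis 2.2, state that the significant treatment effect means this treatment contrast.

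The cost is SAP wording only: the data and the planned modelling approach stay the same, and a different contrast is declared primary. The change should be dated and made before outcomes are seen by arm. If they have been seen already, report both tests and say so.
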